**Table 6-2 Clinically relevant drug interactions: inducers, and inhibitors of isoenzyme CYP3A**

Inducers
Strong inducers: avasimibe, carbamazepine, mitotane, phenobarbital, phenytoin, rifabutin, rifampin (rifampicin), St. John's wort (hypericum perforatum)
Moderate inducers: bosentan, efavirenz, etravirine, genistein, modafinil, naftillin, ritonavir, [talviraline], thioridazine, tipranavir
Weak inducers: amprenavir, aprepitant, armodafinil (R-modafinil), bexarotene, clobazam, danshen, dexamethasone, Echinacea, garlic (allium sativum), gingko (ginkgo biloba), glycyrrhizin, methylprednisolone, nevirapine, oxcarbazepine, pioglitazone, prednisone, [pleconaril], primidone, raltegravir, rufinamide, sorafenib, telaprevir, terbinafine, topiramate, [troglitazone] , vinblastine
Inhibitors
Strong inhibitors: boceprevir , clarithromycin, cobicistat, conivaptan, elvitegravir, indinavir, itraconazole, ketoconazole, lopinavir, mibefradil, nefazodone, neflifavir, posaconazole ( Krishna et al 2009 ), ritonavir, saquinavir, telaprevir , telithromycin, tipranavir, troleandomycin, voriconazole
Moderate inhibitors: Amprenavir, aprepitant, atazanavir, casopitant, cimetidine, ciprofloxacin, cyclosporine, darunavir, diltiazem, dronedarone, erythromycin, fluconazole, fosamprenavir, grapefruit juice (citrus parasida fruit juice), imatinib, schisandra sphenanthera, tofisopam, verapamil

**Table 6-3 Clinically relevant drug interactions: substrates, inducers, inhibitors of PgP and PgP/CYP3A dual inhibitors**

Substrates
digoxin, fexofenadine, indinavir, vincristine, colchicine, topotecan, paclitaxel, talinolol, everolimus
Inducers
rifampin, St John's wort
PgP Inhibitors and PgP/CYP3A Dual Inhibitors

amiodarone, azithromycin, captopril, carvedilol, clarithromycin, conivaptan, diltiazem, dronedarone, elacridar, erythromycin, felodipine, fexofenadine, fluvoxamine, gingko (ginkgo biloba), indinavir, itraconazole, lopinavir, mibefradil, milk thistle (silybum marianum), neflifavir, nifedipine, nitrendipine, paroxetine, quercetin, quinidine, ranolazine, rifampin, ritonavir, saquinavir, Schisandra chinensis, St John's wort (hypericum perforatum), talinolol, Telaprevir, telmisartan, ticagrelor, tipranavir, tolvaptan, valspar, verapamil

Reference: Internal Clinical Pharmacology Drug-drug interaction (DDI) memo, updated 29-Oct-2012 which summarizes DDI data from three sources including the FDA's "Guidance for Industry, Drug Interaction Studies", the University of Washington's Drug Interaction Database, and Indiana University School of Medicine's Drug Interaction Table.

## Vaccinations

The use of live vaccines and close contact with those who have received live vaccines should be avoided during treatment with everolimus. Examples of live vaccines are: intranasal influenza, measles, mumps, rubella, oral polio, BCG, yellow fever, varicella, and TY21a typhoid vaccines.

For further details please refer to the current everolimus IB.

#### **6.4.3 Prohibited concomitant therapy**

Treatment with systemic anticancer agents (chemotherapy, hormone therapy, targeted or biologic agents) other than everolimus is not permitted until disease progression is documented and everolimus is permanently discontinued.

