## Glossary of terms

Assessment	A procedure used to generate data required by the study
Control drug	A study treatment used as a comparator to reduce assessment bias, preserve blinding of investigational drug, assess internal study validity, and/or evaluate comparative effects of the investigational drug
Cycles	Number and timing or recommended repetitions of therapy are usually expressed as number of days (e.g.: every 28 days)
Dose level	The dose of drug given to the patient (total daily dose)
Enrollment	Point/time of patient entry into the study; the point at which informed consent must be obtained (i.e. prior to starting any of the procedures described in the protocol)
Investigational treatment	Drug whose properties are being tested in the study. This also includes approved drugs used outside of their indication/approved dosage, or that are tested in a fixed combination. Investigational treatment generally does not include other study treatments administered as concomitant background therapy required or allowed by the protocol when used in within approved indication/dosage
Other study treatment	Any drug administered to the patient as part of the required study procedures that was not included in the investigational treatment
Patient Number (Patient No.)	A unique identifying number assigned to each patient/subject/healthy volunteer who enrolls in the study
Roll-over study	A roll-over study allows patients from multiple parent studies spanning multiple indications to continue to be treated within one study after the completion of the parent study(ies)
Study treatment	Includes any drug or combination of drugs in any study arm administered to the patient (subject) as part of the required study procedures, including placebo and active drug run-ins. In specific examples, it is important to judge investigational treatment component relationship relative to a study treatment combination; study treatment in this case refers to the investigational and non-investigational treatments in combination.

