## 2.4 Rationale for choice of combination drugs

Patients may be allowed to continue combination with everolimus in combination with other therapies if they are currently receiving the therapies on the parent protocol and are driving benefit judged by the investigator.

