## 6 Treatment

### 6.1 Study treatment

For study treatment refer to everolimus plus combination drugs used in the parent study and for investigational treatment refer to everolimus.

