### **6.1.6     Other study treatment**

Please refer to the parent protocol and Package Insert for treatment, management of toxicities and dose modifications.

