## **6.4 Concomitant medications**

### **6.4.1 Permitted concomitant therapy**

In general, concomitant medications/therapies deemed necessary for the supportive care of the patient is permitted.

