#### **6.6.3.3 Handling of other study treatment**

Not applicable.

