### **8.2.2    Reporting**

To ensure patient safety, every SAE, regardless of suspected causality, occurring after the patient has provided informed consent and until at least 30 days after the patient has stopped study treatment must be reported to Novartis within 24 hours of learning of its occurrence.

Any SAEs experienced after this 30 days period should only be reported to Novartis if the investigator suspects a causal relationship to the study treatment. Recurrent episodes, complications, or progression of the initial SAE must be reported as follow-up to the original episode within 24 hours of the investigator receiving the follow-up information. A SAE occurring at a different time interval or otherwise considered completely unrelated to a previously reported one should be reported separately as a new event.

Information about all SAEs is collected and recorded on the SAE Report Form; all applicable sections of the form must be completed in order to provide a clinically thorough report. The investigator must assess and record the relationship of each SAE to each specific study treatment (if there is more than one study treatment), complete the SAE Report Form in Japanese, and send the completed, signed form by fax within 24 hours to the Novartis Drug Safety and Epidemiology (DS&E) department.

The telephone and telefax number of the contact persons in the local department of DS&E, specific to the site, are listed in the investigator folder provided to each site. The original copy of the SAE Report Form and the fax confirmation sheet must be kept with the CRF documentation at the study site.

Follow-up information is sent to the same contact(s) to whom the original SAE Report Form was sent, using a new SAE Report Form stating that this is a follow-up to the previously reported SAE and giving the date of the original report. Each re-occurrence, complication, or progression of the original event should be reported as a follow-up to that event regardless of when it occurs. The follow-up information should describe whether the event has resolved or continues, if and how it was treated, whether the blind was broken or not, and whether the patient continued or withdrew from study participation.

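### Section 6.4.3 bars every systemic anticancer drug except everolimus, which contradicts Sections 2.4 and 6.1, where combination drugs from the parent study may continue and are part of study treatment

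*Protocol*

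**What the plan says.** Protocol Section 6.4.3 names four classes of systemic anticancer agent (chemotherapy, hormone therapy, targeted agents and biologics) and says that treatment with any of them "other than everolimus is not permitted until disease progression is documented and everolimus is permanently discontinued".

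Two other sections treat combination drugs as part of the regimen:

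- Section 2.4: "Patients may be allowed to continue combination with everolimus in combination with other therapies". The conditions are that the patient is receiving those therapies on the parent protocol and that the investigator judges there to be benefit.
- Section 6.1: "For study treatment refer to everolimus plus combination drugs used in the parent study and for investigational treatment refer to everolimus".

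Two more sections fit with partner drugs being taken, though they do not grant permission:

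- Section 6.1.6, on other study treatment: "Please refer to the parent protocol and Package Insert for treatment, management of toxicities and dose modifications".
- Section 8.2.2, which asks the investigator to assess the "relationship of each SAE to each specific study treatment (if there is more than one study treatment").

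**The concern.** A patient may roll over on everolimus plus an anticancer partner. Section 2.4 says that the combination may go on, while Section 6.4.3 says that the partner may not be given. A site that obeys 6.4.3 stops one component of a regimen from which the patient is, by the inclusion criteria, benefiting. A site that obeys 2.4 and 6.1 breaches 6.4.3. Different sites could choose differently.

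The consequences are set out elsewhere in the protocol. Section 12 allows no authorised deviations and sends significant ones to the Clinical Study Report. Section 7.1.4.1 lists protocol deviation among the reasons for which a patient may be withdrawn. The adverse event tables (Protocol Section 10.4.2, SAP Section 1.2.1) are broken down by relation to study treatment, so what patients may take as study treatment ought to be unambiguous.

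**Working it through.** There is no figure to reproduce: the protocol sets no sample size, alpha or power, and the point rests on none. The check is to set the sections side by side.

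**Step 1: what 6.4.3 permits.** Another anticancer agent may be given only if (a) progression is documented and (b) everolimus is permanently discontinued. Both must hold. Giving a partner together with everolimus means that (b) is false, so concurrent use is never permitted, whatever the state of (a).

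**Step 2: compare with the other sections, for an anticancer partner continued from the parent study.**

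| Section | Partner drug taken with everolimus |
|---|---|
| 6.4.3 | Not permitted |
| 2.4 | May continue, if benefit is judged present |
| 6.1 | Part of study treatment by definition |
| 6.1.6 | Managed under the parent protocol and Package Insert |
| 8.2.2 | Causality assessed separately, if there is more than one study treatment |

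The first row conflicts with the second and third. The last two rows are indirect support only.

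**Step 3: look for an exception within 6.4.** Section 6.4.1 says that "concomitant medications/therapies deemed necessary for the supportive care of the patient is permitted", which covers supportive care and not anticancer treatment. Section 6.4.2, with its two tables and the vaccination text, deals with CYP3A and PgP interactions and live vaccines. Section 6.4.3 exempts everolimus alone. None of the three subsections exempts a continued partner drug. Little weight falls on 6.4.2, where one would not expect such an exception.

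**Step 4: look for a restriction elsewhere that would remove the conflict.** Section 2.4 does not limit the continued therapies to non-anticancer drugs. Section 6.6.3.3, "Handling of other study treatment", is marked not applicable, but it belongs to drug accountability and does not say whether a partner may be taken.

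**Step 5: is the case real or only logical?** Section 1.2.1.2 says that everolimus has been developed both alone and with antitumor agents. It also records the approved combination with exemestane in hormone receptor-positive breast cancer, in countries including Japan. Exemestane is a hormone therapy, a class that 6.4.3 names. So such partners exist in the programme. This does not show that any such patient enters this study.

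**The case against.** The best defence is structural. Section 6.4 is about concomitant medication, whereas Section 6.1 places the combination drugs in a different class, study treatment, and 6.1.6 sends the site to the parent protocol for their management. On that view 6.4.3 governs only therapy that is added, and an investigator who reads the whole protocol would probably take it so.

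This is a fair account of what may have been intended, but the wording does not carry it. Everolimus is itself study treatment, yet 6.4.3 exempts it by name. If study treatment already lay outside the rule, that exemption would be unnecessary. The glossary also speaks of "other study treatments administered as concomitant background therapy required or allowed by the protocol", so a study treatment can be concomitant in the protocol's own vocabulary. That last point is minor, because the phrase comes from the definition of investigational treatment and assumes that the therapy is allowed.

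Several limits stand:

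- Section 6.1 is a definition. The permission itself comes from Section 2.4, a rationale section with permissive wording.
- Section 8.2.2 is weak support. Its wording is conditional and looks like template text, since the same section asks about breaking the blind in an open-label study.
- The sponsor chooses the parent studies and the documents do not list them, so there may be no affected patient.
- Harm requires a site to apply 6.4.3 literally without asking which section governs. Section 12 forbids asking the sponsor to approve a deviation, but it does not forbid asking for clarification.
- Only significant deviations are reported in the Clinical Study Report, and withdrawal is optional.

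These points limit the consequences. They do not reconcile the sections.

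**Conclusion.** The concern holds. For a continued partner drug that is a systemic anticancer agent, Section 6.4.3 cannot be followed together with Sections 2.4 and 6.1. Partners that are not anticancer agents are unaffected.

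The practical size is unknown and may be nil, and no estimate is made. No bias in the descriptive safety analysis is claimed. The conclusion rests on the current protocol text alone and assumes only that at least one eligible parent study could include an anticancer partner. It should be corrected because 6.4.3 is an operative treatment rule that is wrong as written. The harm is limited and avoidable, so this is a point to fix and not a critical flaw.

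**What to change.** Amend the exemption in Section 6.4.3 to read: *other than everolimus and any combination drugs continued from the parent study (Sections 2.4 and 6.1)*. The bar on starting any other anticancer agent stays in force, and no other section has to change. The cost is one clause in a protocol amendment, with no effect on visits, data collection or analysis.

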### **6.5 Patient numbering, treatment assignment or randomization**

#### **6.5.1 Patient numbering**

Each patient is identified in the study by a Subject Number (Subject No.), that is assigned when the patient is first enrolled in the roll-over study and is retained as the primary identifier for the patient throughout his/her entire participation in the trial. The Subject No. consists of the Center Number (Center No.) (as assigned by Novartis to the investigative site) with a sequential patient number suffixed to it, so that each subject is numbered uniquely across the entire database. .

Additionally an electronic Case Report Form (eCRF) will be completed that identifies the patient by gender and date of birth and previous study, site/center and subject number.

#### **6.5.2 Treatment assignment or randomization**

All consented patients who meet all inclusion criteria and none of the exclusion criteria are eligible to receive everolimus.

#### **6.5.3 Treatment blinding**

Not applicable.

### **6.6 Study drug preparation and dispensation**

The investigator or responsible site personnel must instruct the patient or caregiver to take the study drugs as per protocol. Study drug(s) will be dispensed to the patient by authorized site personnel only. All everolimus dosages prescribed to the patient and all dose changes during the study must be recorded on the Everolimus Dosage Administration Record eCRF.

**Table 6-4 Preparation and dispensing**

Investigational treatments	Dispensing	Preparation
Everolimus	Blister packed tablets (2.5 – 5 mg) including instructions for administration will be dispensed by study personnel on an outpatient basis. Patients will be provided with an adequate supply of everolimus for self-administration at home until at least their next scheduled study visit. Dispensing of investigational drug must be managed regularly according to local practice (e.g., every 2 to 3 months).	Not applicable

#### **6.6.1 Study drug packaging and labeling**

Everolimus printed description on patient kit box will be in Japanese and comply with the legal requirements of Japan. They will include storage conditions for the drug but no information about the patient.

Everolimus for the roll-over study can be provided where appropriate as investigational medical products, packed under the responsibility of Novartis Drug Supply Management in Japan.

The remained study drugs of the parent study which satisfies the legal requirements and no change in the description on patient kit box can be used for this roll-over study. More details can be found in the study drug manual of CRAD001C1X01B.

**Table 6-5 Packaging and labeling**

Investigational treatment	Packaging	Labeling (the printed description on patient kit's box)
Everolimus	Tablets in blisters	As per local requirements

### **6.6.2 Drug supply and storage**

Everolimus must be received by designated personnel at the study site, handled and stored safely and properly, and kept in a secured location to which only the investigator and designated site personnel have access. Upon receipt, everolimus should be stored according to the instructions specified on the drug labels and in the current everolimus IB.

**Table 6-6 Supply and storage of Investigational treatments**

Investigational treatments	Supply	Storage
Everolimus	Local clinical study supply (open label) supplied by Novartis	Refer to everolimus printed description on patient kit box

### **6.6.3 Study drug compliance and accountability**

#### **6.6.3.1 Study drug compliance**

Compliance will be assessed by the investigator and/or study personnel at each patient visit and information provided by the patient and/or caregiver will be captured in the Drug Accountability Form. This information must be captured in the source document at each patient visit.

#### **6.6.3.2 Study drug accountability**

The investigator or designee must maintain an accurate record of the shipment and dispensing of everolimus in a drug accountability log. Drug accountability will be noted by the field monitor during site visits and at the completion of the study. At study close-out, and, as appropriate during the course of the study, the investigator will return all used and unused everolimus, packaging, drug labels, and a copy of the completed drug accountability log to the Novartis monitor or to the Novartis address provided in the investigator folder at each site.

#### **6.6.3.3 Handling of other study treatment**

Not applicable.

#### **6.6.4 Disposal and destruction**

At study close-out, and, as appropriate during the course of the study, the investigator will return all used and unused everolimus, packaging, the patient kit's box, and a copy of the completed drug accountability log to the Novartis monitor.

The study drug supply can be destroyed at the local Novartis facility, Drug Supply group or third party, as appropriate.

### **7 Visit schedule and assessments**

#### **7.1 Study flow and visit schedule**

Table 7-1 lists all of the assessments and indicates with an “X”, the visits when they are performed. All data obtained from these assessments must be supported in the patient's source documentation. Patients must return to the study center at least yearly ( $\pm$  3 months) for resupply of study medication.

The table indicates which assessments produce data to be entered into the clinical database (D) or documented at the site level in the source documents (S) (“Category” column).

**Table 7-1** Visit evaluation schedule

### **7.1.1 Enroll visit**

There will be no screening period for this study. At the enrollment visit, the patient will need to complete a written informed consent. Once consented, patients will be evaluated for eligibility via the inclusion and exclusion criteria.

#### **7.1.1.1 Eligibility screening**

Not applicable.

#### **7.1.1.2 Information to be collected on screening failures**

Not applicable.

#### **7.1.1.3 Patient demographics and other baseline characteristics**

For patients who are eligible to participate in this roll over study, an eCRF will be completed that identifies the patients' race, gender, date of birth and previous study, site/center and subject number.

### **7.1.2 Run-in period**

Not applicable.

### **7.1.3 Treatment period**

The starting dose of everolimus on this roll-over protocol should be the same dose as that which the patient was receiving in the parent study at roll over.

At least, patients must return to the study center on a yearly basis ( $\pm$  3 months), but for resupply of study medication, the frequency of the receipt and dispensing must follow local practice (e.g., every 2 to 3 months). At this time the dose of everolimus is based on the investigator's judgment.

Patient whose treatment is interrupted or permanently discontinued due to an AE or clinically significant laboratory value, should be followed up at least once a week (or more frequently if clinically indicated) for 4 weeks, and subsequently at approximately 4-week intervals, until resolution or stabilization of the event, whichever comes first.

The study is expected to remain open for 5 years or until such time that enrolled patients no longer need treatment with everolimus, whichever comes first.

### **7.1.4 End of treatment visit including study completion and premature withdrawal**

Patients will continue to be treated until they are no longer benefiting from everolimus treatment, develop unacceptable toxicities, withdraw consent, are non-compliant to the protocol, or the patient dies, whichever comes first.

At the time the patient discontinues study treatment, a visit should be scheduled as soon as possible, at which time the End of Treatment visit will be performed. End of Treatment information will be completed in the eCRF giving the date and reason for stopping the study treatment.

At a minimum, all patients who discontinue study treatment, including those who refuse to return for a final visit, will be contacted for the required safety evaluation during the 30 days after the last dose of everolimus.

Patients who discontinue study treatment should be considered withdrawn from the study after the final visit assessments are performed or when it is clear that the patient will not return for these assessments.

If a study withdrawal occurs, or if the patient fails to return for visits, the investigator must determine the primary reason for a patient's withdrawal from the study and record this information on the appropriate eCRF page.

A patient will reach the end of study when everolimus treatment is permanently discontinued and there will be **no** further follow-up study visits. Thirty-day safety follow-up could be done via a phone contact.

